# 5.5. Treatment Effect (Durability of Hematologic Effect)

Descriptive summaries of hemoglobin, indirect bilirubin, % reticulocytes, and absolute reticulocytes for all participants at GBT440-034 baseline and each evaluation post baseline through Week 48, as well as changes from baseline over time, will be provided. Laboratory assessments within 8 weeks post RBC transfusion, for any reason, will be imputed by the last laboratory value prior to the transfusion.

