8.5. Missing, Unused, or Spurious Data

Data will be summarized as observed with no imputation for missing values, excepting partially missing dates. Full details of how missing date data will be handled will be described in the SAP.

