- e. Serum chemistries will include: Alanine aminotransferase (ALT), alkaline phosphatase (ALK), aspartate aminotransferase (AST), bicarbonate, BUN, creatinine, LDH, sodium, potassium, bilirubin (total, direct, and indirect). After Week 48, serum chemistries should only be performed per standard of care.
- f. After Week 48 (for participants enrolled outside of the United States and Europe), laboratory values for measures of hemolysis such as hemoglobin, % reticulocytes, absolute reticulocytes, and bilirubin (total, direct, and indirect) will be collected every 24 weeks.
- g. If a urine pregnancy test is positive, the result must be confirmed per local standard of care (eg. ultrasound or serum pregnancy test).
- h. Voxelotor will be dispensed in 12-week (~90 day) intervals with instruction to participants to return any used/unused bottles to clinic.
- The End of Study (EOS) visit should be conducted within 28-35 days after last dose of study drug for participants who withdraw from the study early.

The EOS visit can occur any time after participants obtains commercial voxelotor for participants who complete study per protocol. Participants who complete study per protocol should remain on study drug until EOS visit is completed.

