# 2.1. Study Design

Study GBT440-034 is a multicenter, global, open-label extension (OLE) study available to participants who were previously enrolled and treated in Study GBT440-031. Participants must meet the entry criteria for this study to be eligible for enrollment.

All participants enrolled in GBT440-034, regardless of treatment received in the parent study GBT440-031 (i.e., placebo, voxelotor 900 mg, or voxelotor 1500 mg), receive treatment with voxelotor 1500 mg once daily (the highest dose deemed safe for continued assessment based on GBT440-031).

All participants in Study GBT440-034 have scheduled study visits with assessments at Day 1, Week 12, Week 24, and Week 48, and then every 24 weeks thereafter. Participants who were treated with placebo or voxelotor 900 mg in Study GBT440-031 have additional study visits with assessments at Week 4 and Week 8.

Participants may receive voxelotor in GBT440-034 as long as they continue to receive clinical benefit which outweighs risk as determined by the Investigator and/or until the participant has access to voxelotor from an alternative source (i.e., commercialization or through a managed access program).

Additional details and background information are provided in the study protocol.

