## **Study Completion**

Completion of study is specified on the EOS case report form (CRF). Participants are considered to have completed the study if they end study participation to transition to voxelotor from an alternative source (i.e., commercialization or through a managed access program). Participants who end study participation for any other reason (e.g., adverse event, withdrawal of consent, lost to follow-up, study terminated by sponsor) are considered to have discontinued the study early.

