#### 3.2. Visit Windows

For summaries by timepoint (e.g., laboratory values and vital signs), analysis visit windows will be used to classify assessments based on the actual treatment day of the measurement regardless of the original nominal visit label. This includes assessments collected at Unscheduled or EOS visits. Target study days, the protocol-specified study day windows, and the analysis visit windows are shown in Table 1.

**Table 1:** Analysis Windows

Timepoint	Target Study Day (relative to first dose)	Visit Window per Protocol (treatment days)	Window for Statistical Analysis (treatment days)
Baseline	1		Last value a taken on or prior to date of first dose in GBT440-034
Week 4	28	[23, 33]	[2, 42]
Week 8	56	[51, 61]	[43, 70]

Timepoint	Target Study Day (relative to first dose)	Visit Window per Protocol (treatment days)	Window for Statistical Analysis (treatment days)		
Week 12	84	[79, 89]	[71, 126]		
Week 24	168	[158, 178]	[127, 252]		
Week 48	336	[326, 346]	[253, 420]		
Week 72	504	[494, 514]	[421, 588]		
Week 96	672	[662, 682]	[589, 756]		
Week 120	840	[830, 850]	[757, 924]		
Week 144	1008	[998, 1018]	[925, 1092]		
Week 168	1176	[1166, 1186]	[1093, 1260]		
Week 192	1344	[1334, 1354]	[1261, 1428]		
	< Continues with 24-week intervals >				

Note: If multiple measurements fall within the statistical analysis window, the average of the measurements will be used.

Note that per the protocol Schedule of Assessments, laboratory assessments and vital signs are collected at visits up to Week 48. After Week 48, laboratory assessments are collected per standard of care for clinical management with the following exception: for participants enrolled outside of the US and Europe, hemoglobin and clinical measures of hemolysis (% reticulocytes, absolute reticulocytes, and bilirubin [total, direct, and indirect]) are collected after Week 48 at 24-week intervals (see Section 5.4.3).

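### SAP 5.5's by-visit hematology means mix change within participants with change in who is measured, and no planned analysis separates the two

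*SAP*

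**What the plan says.** - **The analysis.** SAP 5.5 plans descriptive summaries of hemoglobin, indirect bilirubin and reticulocytes (percent and absolute) "for all participants at GBT440-034 baseline and each evaluation post baseline through Week 48, as well as changes from baseline over time". SAP 4.2 adds presentation by prior treatment group, as appropriate.
- **Missing data.** Protocol 8.5: "Data will be summarized as observed with no imputation for missing values", partial dates excepted. The SAP gives no other rule for missed visits. Its one imputation in this section concerns transfusion: values in the 8 weeks after a red cell transfusion "will be imputed by the last laboratory value prior to the transfusion". That does not cover people who have left.
- **Who stays.** SAP 2.1 lets participants receive voxelotor "as long as they continue to receive clinical benefit which outweighs risk as determined by the Investigator". The same sentence sets a second limit, as an addition or an alternative to the first: "until the participant has access to voxelotor from an alternative source". The second route is the definition of finishing the study (SAP 3.1): "Participants are considered to have completed the study if they end study participation to transition to voxelotor from an alternative source".
- **Which values count.** SAP 3.2 assigns values to windows by actual treatment day: "This includes assessments collected at Unscheduled or EOS visits". Several values in one window are averaged. Under Protocol Appendix 1, the EOS "visit should be conducted within 28-35 days after last dose of study drug for participants who withdraw from the study early", and hematology is drawn at it. Those who complete by transition stay on drug until EOS.
- **Who is scheduled.** Week 4 and Week 8 apply to participants from placebo or 900 mg (SAP 2.1). Protocol 7.1 and Appendix 1 add those with less than 12 weeks of prior treatment.
- **Attrition.** SAP 5.1 tabulates disposition and reasons for stopping, but nothing links them to hematology.

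**The concern.** Durability asks whether the effect persists within the same people. A series of available-case means answers that only if those measured at each visit are comparable. Here they are not. The set scheduled at Weeks 4 and 8 differs from the set at Week 12, and the reasons for leaving afterwards can be related to hemoglobin response.

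Everything is descriptive (SAP 5), so these tables are the whole of the durability evidence. No model or test will later correct a misleading trend. A flat mean could hide waning, and a falling mean could show waning that did not occur. The planned outputs would not tell the reader which.

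**Working it through.** **Inputs.** The documents state no effect size, standard deviation, attrition rate or expected Week 48 mean, so there is no figure of the plan to reproduce. The 274 in SAP 2.3 is a cap. All rates below are assumptions, used to show direction and range.

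**1. Membership change by design.** Suppose three equal prior-treatment groups. The ex-placebo group changes by +0.90 g/dL and the other two by 0, nobody leaves, and those with under 12 weeks of prior treatment are ignored.
- Week 8 (ex-placebo and ex-900 mg): (0.90 + 0)/2 = 0.45.
- Week 12 (all three): (0.90 + 0 + 0)/3 = 0.30.

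The overall mean falls by 0.15 with no participant changing. Tables by prior group would remove most of this.

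**2. Exit related to response.** Let pR and pN be the shares of responders and non-responders, lR and lN the fractions gone before Week 48, and mR and mN the mean changes.

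Observed mean = [pR(1-lR)mR + pN(1-lN)mN] / [pR(1-lR) + pN(1-lN)]

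Take pR = 0.6, mR = +1.5, pN = 0.4, mN = 0. The full-cohort mean is 0.6 × 1.5 = 0.90.

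| lR / lN | Observed at Week 48 | Distortion |
|---|---|---|
| 10% / 30% | 0.81/0.82 = 0.99 | +0.09 |
| 10% / 50% | 0.81/0.74 = 1.09 | +0.19 |
| 20% / 20% | 0.72/0.80 = 0.90 | 0 |
| 30% / 10% | 0.63/0.78 = 0.81 | -0.09 |
| 50% / 10% | 0.45/0.66 = 0.68 | -0.22 |

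The last two rows are the pattern expected if benefiting participants move to another source.

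**3. With true waning, and what a fixed cohort shows.** Let nobody leave by Week 24 (mean 0.90), and let the true Week 48 changes be +1.2 and -0.2. The full-cohort mean is then 0.72 - 0.08 = 0.64, a true decline of 0.26.
- Exits 5% / 70%: observed Week 48 = (0.684 - 0.024)/0.69 = 0.96. The series goes from 0.90 to 0.96, an apparent rise. In the same stayers, Week 24 was 0.855/0.69 = 1.24, so the fixed cohort falls from 1.24 to 0.96, or -0.28.
- Exits 30% / 10%: observed Week 48 = (0.504 - 0.072)/0.78 = 0.55. The series falls by 0.35. In the stayers, Week 24 was 0.63/0.78 = 0.81, so the fixed cohort falls by 0.25 (0.198/0.78).

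In both cases the fixed cohort recovers the decline closely. Its level (1.24 or 0.81, against 0.90) is not that of all treated participants, so leavers need their own summary.

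**4. Off-drug EOS values.** Return to the 10% / 50% case without waning. If every leaver is an early withdrawal whose EOS value falls in the Week 48 window with change 0, the mean is 0.6 × 0.9 × 1.5 = 0.81 over the whole cohort. That is below 0.90, where step 2 gave 1.09. This is a bounding case: earlier leavers' EOS values fall in earlier windows.

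**5. Dilution by on-drug baselines.** SAP 3.1 takes baseline as the last value up to first dose in this study, including late parent-study visits, and says most participants had already received voxelotor. If one third are ex-placebo, the rest change by about 0, and exit rates are equal across groups, the overall distortion is a third of step 2: +0.19/3 = +0.06 and -0.22/3 = -0.07.

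**The case against.** A reader might infer that durability is overstated, because those who remain are those judged to benefit. The documents do not support that. The continuation rule has a second limb, access to the drug elsewhere. Leaving by it counts as completion, and it can remove people who are doing well. Early withdrawals can also contribute an off-drug value, which pulls the mean down. The Week 48 window is wide (Days 253 to 420), so someone leaving within it may still be represented. For participants already on voxelotor, change from baseline leaves less room for selection on initial response. This part of the objection stands, and no direction can be claimed.

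It can also be said that the study is descriptive, that results are shown by prior treatment group, that reasons for stopping are tabulated, and that the separate table shells may already show n per visit. These points reduce the concern but do not remove it. Tables by prior group deal with the Week 4 and Week 8 membership but not with later exits. A disposition table not linked to hematology cannot show whether leavers had a different response. Distortions of opposite sign and unknown size do not make the mean reliable.

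Lack of benefit is not among the reasons in Protocol 4.3. Such exits may be recorded under investigator discretion or withdrawal of consent, so a summary by reason cannot isolate them fully.

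**Conclusion.** The gap is real but limited. The by-visit, as-observed means in SAP 5.5 combine within-participant change with changing membership, and no planned analysis separates them. The conclusion that durability is overstated does not follow, because sign and size cannot be known from the documents.

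Under the assumed 60/40 response split and the exit rates shown, the distortion is -0.22 to +0.19 g/dL in a group newly starting drug, and roughly -0.07 to +0.06 overall if one third came from placebo. For scale, Protocol 1.3.2 describes an increase above 1 g/dL in the parent study as clinically meaningful. The case for acting rests on the low cost of the remedy and on the absence of any other durability evidence, not on a demonstrated bias.

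**What to change.** Amend SAP 5.5 as follows.

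- **(a) Fixed cohort.** Report n at each visit. Repeat the hemoglobin, indirect bilirubin and reticulocyte summaries, overall and by prior treatment group, for participants with values at baseline and Weeks 12, 24 and 48.
- **(b) Leavers.** For participants who leave before Week 48, summarise the last on-treatment value and its change from baseline by the reason on the CRF, with transition to an alternative source separate from all other reasons. In the by-visit durability summaries, exclude or flag EOS values taken off drug.

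Describe durability from these together with the available-case means. A proportion of participants maintaining their response is not proposed: it would need a definition of maintenance and a rule for transitions, and it would count tolerability stops as loss of hematologic effect.

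The cost is one or two extra descriptive tables from data already collected, with no new test. The fixed cohort is smaller and selected, and the durability figure may turn out less favourable.

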7.1.5. Laboratory Assessments

Central laboratory assessments will be performed for participants enrolled in the United States and Europe.

Local laboratory assessments will be performed by each site's local laboratory for participants enrolled outside of the United States or Europe.

The laboratory parameters listed in the sections below will be assessed. Additional laboratory assessments may be collected as indicated per standard of care for clinical management.

For adolescent participants, the total volume of blood collected for will not exceed the recommended blood sample volume limits outlined in 2010 WHO Guidelines. For this study, 12 years of age is the youngest age to be enrolled, thus total blood volume collection will not exceed 2.4 mL/kg in a given 4 week period, for any adolescent enrolled in the study.

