#### 2. INTRODUCTION

The objective of Study GBT440-034 (C5341022) is to assess the long-term safety and treatment effect of voxelotor in participants with sickle cell disease (SCD) who have completed treatment in Study GBT440-031.

This statistical analysis plan (SAP) provides details of the planned analyses and statistical methods for Study GBT440-034 final clinical study report (CSR). Where this document differs from the high-level analysis plan described in the study protocol, the methodology described in this SAP is considered the latest and supersedes the corresponding section(s) in the protocol.

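### SAP 5.5 overwrites observed labs for 8 weeks after a transfusion with a prior value that may be an acute low, about 24 weeks old, or baseline, and plans no companion summary or count to show the effect

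*SAP*

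**What the plan says.** SAP 5.5 is the treatment-effect analysis. It describes hemoglobin, indirect bilirubin, percent reticulocytes and absolute reticulocytes at the GBT440-034 baseline and at each evaluation through Week 48, with changes from baseline. It then adds: "Laboratory assessments within 8 weeks post RBC transfusion, for any reason, will be imputed by the last laboratory value prior to the transfusion". It does not say how old the prior value may be, whether a sample taken at the acute event qualifies, whether a value still affected by an earlier transfusion qualifies, or how many values are replaced. It plans no alternative handling.

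Which values are available to be carried depends on other sections:

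- Protocol 7.1.5: "Additional laboratory assessments may be collected as indicated per standard of care for clinical management".
- SAP 3.2 assigns results to windows by actual treatment day and adds: "This includes assessments collected at Unscheduled or EOS visits". It also says: "If multiple measurements fall within the statistical analysis window, the average of the measurements will be used".
- SAP 2.1: "All participants in Study GBT440-034 have scheduled study visits with assessments at Day 1, Week 12, Week 24, and Week 48", then every 24 weeks. Participants previously on placebo or 900 mg "have additional study visits with assessments at Week 4 and Week 8". In protocol Appendix 1, Week 36 is a drug-dispensing visit without labs.

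On missing data, protocol 8.5 says: "Data will be summarized as observed with no imputation for missing values, excepting partially missing dates". SAP section 2 says that where the two documents differ, "the methodology described in this SAP is considered the latest and supersedes the corresponding section(s) in the protocol". SAP 5.3.3 separately summarizes hematology and chemistry through Week 48, with no transfusion rule.

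**The concern.** Removing hemoglobin raised by transfused cells from a durability summary is a sensible aim. The difficulty is what takes its place. The rule discards a measured value and substitutes another whose meaning depends on whether a site happened to draw an unscheduled sample. With such a sample, the substitute may be the low that led to the transfusion. Without one, it is the previous scheduled result or baseline.

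The Week 48 case matters most, because Week 48 is the last visit in the 5.5 summary. Copying Week 24 into Week 48 sets that participant's change between the two visits to zero, which assumes the durability that the analysis is meant to assess. The rule also acts unevenly across the prior-treatment groups that SAP 4.2 presents separately, because only some participants have labs at Weeks 4 and 8.

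The study is descriptive, so no test or error rate is affected. The printed means and SDs are the result, however, and a reader of the 5.5 table could not tell how much of a visit's summary was measured at that visit.

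**Working it through.** The plan gives no figure for the effect of this rule, so there is none to reproduce. Two checks are possible.

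**1. Age of the carried value**

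Inputs are the target days and visit windows in SAP Table 1. The windows equal the target day ±5 days through Week 12 and ±10 days from Week 24, matching protocol Appendix 1. The look-back is 8 × 7 = 56 days.

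Nominal age = target day of the replaced visit − target day of the previous scheduled lab. Maximum age = latest allowed day of the former − earliest allowed day of the latter.

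| Replaced visit | Value carried | Nominal age | Maximum within windows |
|---|---|---|---|
| Week 12, no Week 4/8 labs | Day 1 | 84 − 1 = 83 days (11.9 weeks) | 89 − 1 = 88 days (12.6 weeks) |
| Week 12, with Week 4/8 labs | Week 8 | 84 − 56 = 28 days (4.0 weeks) | 89 − 51 = 38 days (5.4 weeks) |
| Week 24 | Week 12 | 168 − 84 = 84 days (12.0 weeks) | 178 − 79 = 99 days (14.1 weeks) |
| Week 48 | Week 24 | 336 − 168 = 168 days (24.0 weeks) | 346 − 158 = 188 days (26.9 weeks) |
| Week 48, Week 24 missed | Week 12 | 336 − 84 = 252 days (36.0 weeks) | 346 − 79 = 267 days (38.1 weeks) |

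A transfusion between day 336 − 56 = 280 (Week 40) and the Week 48 visit triggers the Week 48 replacement. If no unscheduled lab exists, the Week 24 value is already 280 − 168 = 112 days (16 weeks) to 168 days (24 weeks) old at the transfusion.

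In the first row the carried value is the Day 1 sample. The reported change is then zero, or close to it where baseline is an average of several pre-dose records.

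**2. Size of the shift in the mean**

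Shift = p × (carried value − true value), averaged over replaced participants. Here p is the share replaced at the visit, and the true value is the hemoglobin without the transfusion effect. The documents give neither quantity, so both are assumed.

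- All carried values are acute lows, 1–2 g/dL below the true value, p = 10–20%: 0.10 × (−1) = −0.1 to 0.20 × (−2) = −0.4 g/dL.
- Half are acute lows and half are correct: half of that, −0.05 to −0.2 g/dL.
- Stale values from participants who have truly lost 1 g/dL since the carried sample, p = 10–20%: 0.10 × (+1) = +0.1 to 0.20 × (+1) = +0.2 g/dL, so a loss of effect is hidden.

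The sign is therefore not fixed.

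**3. Order of operations**

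SAP 3.2 averages multiple values within a window, and the Week 48 analysis window runs from day 253 to day 420. The SAP does not say whether replacement comes before or after averaging. If averaging comes first, a post-transfusion result can be blended with an unaffected one before the rule is applied. If replacement comes first, each replaced lab becomes another copy of the same prior value in the average. The tables will depend on which is programmed.

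**The case against.** Several points on the other side stand.

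- **Not a protocol breach.** A reader might infer that SAP 5.5 violates protocol 8.5. It does not. The protocol's ban concerns missing values, these are observed values being replaced, and the SAP takes precedence where the two differ. What remains is a departure from summarizing data as observed, with no reason given.
- **The 5.3.3 table is not a contradiction.** A reader might call two differing hemoglobin tables an inconsistency. The 5.3.3 table is a useful as-observed comparison. It cannot replace a set-to-missing summary, though, because it includes the transfusion-raised values.
- **Setting values to missing is not unbiased.** If transfused participants respond less well, dropping them overstates the mean. Assuming 10–20% are dropped and their true change is 0.5–1.0 g/dL lower, the overstatement is 0.10 × 0.5 = 0.05 to 0.20 × 1.0 = 0.20 g/dL. That matches the size of the half-acute case above. Exclusion as the only rule would exchange one bias for another.
- **Acute samples may not be in the data.** Protocol 7.1.5 permits clinical-management labs and SAP 3.2 admits unscheduled ones to the visit summaries. Neither says that hospital counts before a transfusion are entered, and scheduled labs in the US and Europe are central. The acute-low route is possible, not established.
- **Barring acute samples makes staleness more likely.** This is true, and is one reason to show two versions.
- **Counts may be planned in the table shells.** SAP section 6 places these in a separate document. The SAP text itself does not require counts.

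**Conclusion.** The concern holds as a defect of specification and display. As written, SAP 5.5 allows an acute value, a value 168 days old by schedule (188 within windows, longer after a missed visit), or baseline to stand as a measurement at a later visit. The SDs then include values not measured at that visit.

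The ages follow from the SAP's own visit table. The effect on the mean does not: −0.1 to −0.4 g/dL assumes 10–20% replaced and every carried value 1–2 g/dL too low, and −0.05 to −0.2 assumes half are. A stale value can move the mean the other way.

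A reader might set these shifts against the gain of more than 1 g/dL cited in protocol 1.3.2. That figure is a parent-study contrast with placebo, whereas SAP 5.5 measures change from the extension baseline and SAP 3.1 notes that most participants had already received voxelotor. The documents support no such expected change here. Nor do they show that the summary is in fact biased, only that the plan gives no means of telling.

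**What to change.** Amend SAP 5.5 as follows.

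1. State that the rule departs from protocol 8.5, and why.
2. Present the hemoglobin and hemolysis summaries twice: with labs within 8 weeks after transfusion set to missing, and with carry-forward.
3. In the carry-forward version, do not carry values drawn at the event that prompted the transfusion, or values themselves within 8 weeks after an earlier transfusion. Define the first category so that it can be programmed, for example as unscheduled samples within a prespecified number of days before the transfusion.
4. Apply the rule before averaging within a window, and say whether several replaced labs in one window count once or more than once.
5. Print the number of affected values per visit and prior-treatment group.
6. Footnote that the 5.3.3 table is as observed, with no transfusion rule.

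The cost is SAP wording, some programming and one extra table, with no new data. The set-to-missing version has fewer values per visit and may overstate the mean if transfused participants respond less well. The carry-forward version still contains old values. Neither should be read alone: agreement would indicate that the durability result does not depend on the carried values, and disagreement would show by how much it does.
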